### 2.6.2 Randomization

Subjects in each cohort will be randomized 1:1 to either short-duration or long-duration opioid using randomization tables generated by the hospital Investigational Pharmacy. Each subject is assigned the next number. Anesthesia practitioners are instructed on study procedures, and receive a sealed envelope with Group (drug) assignment and group-specific instructions. To ensure full double-blinding, subjects, investigators, and study team members evaluating patients will be blinded to drug treatment. Dropouts (after treatment) will not be replaced, in case this is not random but outcome-related. Enrollment is increased to account for dropouts.

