### 2.6.5 Post-Discharge

Post-discharge care is not altered for purposes of this study. Both groups in both cohorts will receive standard of care post-discharge analgesics as determined by their treating surgeon. These include NSAIDs and opioids (oxycodone, oxycodone+acetaminophen (Percocet, Tylox), hydrocodone+acetaminophen (Norco, Vicodin), tramadol, and codeine+acetaminophen (Tylenol#3)). Selection and quantity of opioids dispensed will be at surgeons' discretion.

Opioids will be dispensed in a medication monitoring system, to measure drug utilization during the 30d post-discharge follow-up period. After discharge, patients record their pain self-assessments, home opioid use, and side effects each day through emailed REDCap or paper surveys, allowing real time data recording. Additional REDCap surveys will be emailed at 6 and 12 mo.

For approximately 30d postop, patients will be queried once daily (evening) regarding pain (average at rest, with activity, with coughing, using NRS), pain relief and pain interference with eight activities of daily living (5-point Likert scale) using the NIH PROMIS Pain Intensity 3A and Pain Interference 6A questionnaires. Recovery is assessed using the QoR-15. Patients also record opioid and non-opioid analgesic use, sedation, and time to return to work and ADLs, and opioid side effects (ORSDS). This electronic-based system has improved daily data capture, improved reliability, and can trigger patient contact if necessary to ensure maximal data capture.

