Postoperative opioid use will be quantified from the medication monitoring system, patients' daily questionnaire, and residual pill counts, and recorded both as the number of tablets used and total morphine equivalents using standard opioid conversion tables.

Recovery from surgery/anesthesia will be assessed at 7d, 14d, 21d, 30d, 6mo and/or 1yr postoperatively, by assessing patient-reported quality of life, functional independence, health status, and ability to return to work and normal activities. We will assess quality of life (Veterans RAND 12-item health survey VR-12, functional independence (Barthel index of activities of daily living, recovery (QoR-15). QoR-15 assesses 5 domains of patient-reported health status: pain, physical comfort, physical independence, psychological support and emotional state using an 11-point numerical rating scale with results summed from 0 (poor recovery) to a maximum of 150 (excellent recovery). These are among the most commonly used instruments, are extensively validated and normed, and are our hospital standards, used locally for several years. Thus we can compare postop with preop metrics, but also with our entire patient database. VR12 is a short form based on the Veterans SF36 version, has 2 domains and 8 dimensions leading to 12 questions, and generates two aggregate summary scores (Physical Component & Mental Component summaries), which are standardized using weights derived from the general population survey and calibrated so that 0.50 is the threshold defining the status of the respondent. Washington University has standing approval ([name]) to use the VR12 and scoring algorithm. The Barthel questionnaire assesses functional independence (able to complete 10 specific normal activities like bathing, feeding, dressing, with any help). It generates a weighted aggregate score 0-100 (100=highest independence). We will evaluate patients' return to employment (defined as work for pay or volunteer work outside home). If applicable, specific questions targeting the reason (pain, addiction, etc) for not returning to work will be asked at 30d, 6mo and 1yr.

Throughout the investigation, any adverse events will be described, recorded and reported according to GCP and IRB regulations.

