### 2.7 Sample size justification

Sample size is based on the primary outcome measure, total 30d post-discharge home opioid use (number of opioid tablets). Based on available reports (Background) and the Preliminary Results, an ideal state of post-discharge opioid use is defined as  $\leq 5$  pills in 30 days. In the Preliminary data, the rate of "high" post-discharge opioid use (defined as  $> 5$  pills in 30d) was 45% in the short-duration opioid group. With a conservative assumption of a relative risk of 65% for the long-duration group (30% rate of "high" opioid use), a total of 300 subjects (150 per group) will be needed to achieve 80% power assuming alpha = 0.05.

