**Aim 3:** Evaluate major and bothersome short-term (before discharge) and intermediate term (1-30d post-discharge) opioid-related side effects with methadone vs short-duration opioids.

Side effects (respiratory-specific events, composite ORSDS) will be compared between the groups using Chi-squared or Fisher exact test, as appropriate, and using logistic models to adjust for important clinical and demographic covariates.

**Aim 4:** Compare overall recovery after surgery/anesthesia with methadone vs short-duration opioids, as defined by changes in reported Health-related Quality of Life, functional independence, and ability to return to work and normal activity.

Overall recovery will be assessed using chi-square tests for categorical outcomes and t-tests for continuous outcomes as well as a repeated measures model to adjust for multiple time points.

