### **3.0 Recruitment strategy and feasibility**

Subjects will be 18-65 yr. Because this is the first evaluation of methadone for outpatient anesthesia, children and older patients will not be studied (because of declining methadone elimination and increased risk of respiratory depression with age). Such studies may ensue after safety is established in the present investigation. Sample size calculations show that 300 evaluable (completing 30d follow-up) patients are needed in each of the 2 study cohorts (600 total). Change in scheduled operation, prolonged ( $>1$ d) stay of scheduled short-stay (next day discharge) patients, unanticipated admission of same-day patients, or patient withdrawal has occurred in  $\sim 10\%$  of our study patients to date. This, combined with post-op loss to follow-up (see below), suggests a potential overall drop-out rate before completion of 30d follow-up of  $<15\%$ . Hence, to ensure 300 pts evaluable at 30d, a conservative 25% drop-out is estimated and 375 pts in each of the 2 study cohorts will be randomized (750 total). The Duke Department of Anesthesiology provides anesthetics for  $>66,000$  procedures per year. The main campus of Duke University Health System includes Duke University Hospital which is a 957 bed facility. In 2016 there were 41,408 patients admitted and 1,119,151 outpatient visits. Duke University Hospital includes the Duke North Hospital/Duke Medical Pavilion ( $\sim 54$  ORs), the Children’s Health Center, the Duke Eye Center (6 ORs), and Ambulatory Surgery Center (9 ORs). Between the Duke North Hospital/Duke Medical Pavilion and Ambulatory Surgery Center there were 34,492 anesthetics performed in 2017. These included, for example, 375 laparoscopic cholecystectomies and 269 laparoscopic hysterectomies  $\pm$  salpingoophorectomies, further supporting specific feasibility. If enrollment lags, or for strategic advantage, Duke Regional and/or Duke Raleigh Hospitals can be added as future sites.

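### Time to return to work is right-censored, but Aim 4 gives it no time-to-event method and no denominator of patients working before surgery

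*Combined protocol and SAP*

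**What the plan says.** - **Data collected as a time.** Section 2.6.5 (Post-Discharge) has patients report every evening for about 30 days; among the items is "time to return to work and ADLs, and opioid side effects (ORSDS").
- **Definition.** Section 2.6.7 (Observations and Measurements) evaluates "return to employment (defined as work for pay or volunteer work outside home"). It gives no denominator. It asks for reasons for not returning, where applicable, at 30 days, 6 months and 1 year. Section 5.2 says the 6- and 12-month surveys ask about return to work again.
- **Baseline.** Section 2.6.3 records employment before surgery, but no analysis set is built on it.
- **Status of the outcome.** Section 2.6.8 lists return to work within exploratory outcome 16, quality of recovery at visits from day 7 to month 12. Section 2.8 makes it part of the Aim 4 definition of recovery.
- **Method.** Section 2.8, Aim 4: "Overall recovery will be assessed using chi-square tests for categorical outcomes and t-tests for continuous outcomes". The same sentence adds a repeated measures model for the several time points. A survival model and a rule for censoring drop-outs appear only under Aim 1, for stopping opioids.

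**The concern.** A patient not back at work when the diary ends has no observed return time; it is known only to exceed about 30 days. Someone who stops the diary on day 12 without having returned is known only to exceed 12. A t-test has no place for such values unless a rule is added, and a chi-square at a fixed day discards the timing. The repeated measures model can describe status at several visits, but it does not analyse a censored time.

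The denominator is a second gap. Patients with no job or volunteer role before surgery cannot return to one, and the plan does not say whether they are left out, counted as returned or counted as not returned.

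The analyst therefore has to choose among several analyses after the data are in, and the choices differ in power and in what they estimate. At stake is a real gain of a few days in return to work being understated or missed. The weakest choice, comparing only those who returned, also selects patients on an event after randomisation. That runs against the position in Aim 1 that opioid-use analyses should not be confined to completers.

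**Working it through.** **1. The plan's own figure.** The plan states no power for return to work. Its only calculation is for the primary outcome: "a total of 300 subjects (150 per group) will be needed to achieve 80% power assuming alpha = 0.05". The control rate "was 45% in the short-duration opioid group", with "a conservative assumption of a relative risk of 65% for the long-duration group", gives 0.45 × 0.65 = 29.25%. With n = [1.960√(2p̄q̄) + 0.842√(p₁q₁ + p₂q₂)]² / (p₁ − p₂)² and p̄ = 0.37125, this is (1.339 + 0.567)² / 0.1575² ≈ 147 per arm, 294 in total, with 80.9% power at 150 per arm. The stated figure is reproduced at the unrounded rate. I take 150 per arm from it.

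**2. Assumed inputs.** The documents give no employment rate, return rate or effect for this outcome. Assumed: 75% working or volunteering before surgery (112.5 per arm); exponential return times; medians of 8 vs 6, 12 vs 9 or 20 vs 15 days (hazard ratio 4/3 in each); two-sided 0.05; no diary drop-out.

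**3. Fraction back by day 30**, 1 − 2^(−30/median):

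| Medians (days) | Control | Methadone |
|---|---|---|
| 8 vs 6 | 92.6% | 96.9% |
| 12 vs 9 | 82.3% | 90.1% |
| 20 vs 15 | 64.6% | 75.0% |

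**4. Closed-form check at 12 vs 9 days.**
- Log-rank in workers: events = 112.5 × (0.823 + 0.901) = 194; z = ln(4/3) × √(194/4) = 2.00; power = Φ(2.00 − 1.96) ≈ 52%.
- Day-30 chi-square in workers: difference 0.0776, p̄ = 0.862, SE = √(2 × 0.862 × 0.138 / 112.5) = 0.046; z = 1.69; power ≈ 39%.
- Day-30 chi-square in all patients, non-workers counted as not returned: rates 0.75 × 0.823 = 61.7% and 0.75 × 0.901 = 67.6%; difference 0.058, SE = √(2 × 0.6465 × 0.3535 / 150) = 0.055; z = 1.05; power ≈ 18%.

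**5. Simulated power, times in whole days.**

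| Analysis | 12 vs 9 days | Range over the three pairs |
|---|---|---|
| Log-rank, prior workers | 51% | 44-56% |
| t-test, times capped at day 30, workers | 48% | 39-54% (with next row) |
| Repeated status at visits, workers | 47% | 39-54% (with row above) |
| Chi-square at day 30, workers | 39% | 31-40% |
| t-test, returners only | 17% | 9-31% |
| Chi-square, all patients, non-workers counted as not returned | 19% | 8-29% |

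These agree with step 4. Repeat runs moved single entries by up to about 3 points, so gaps of that size should not be over-read.

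**6. Size of the apparent effect at 12 vs 9 days.** With λ = ln 2 / median and S = 2^(−30/median), S is 0.177 and 0.099.
- Restricted mean to day 30, (1 − S)/λ: 14.25 vs 11.70 days, a difference of about 2.6 (about 2.5 with whole-day recording).
- Mean among those back by day 30, (restricted mean − 30S)/(1 − S): 10.9 vs 9.7 days, a difference of about 1.2.

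The returners-only comparison shows about half the gain.

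**7. Sensitivity to the return rate.** Hazard ratio 1.4, 70% working before surgery, power (%) by the share of control workers back by day 30:

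| Analysis | 50% | 70% | 80% | 90% | 95% |
|---|---|---|---|---|---|
| Log-rank, workers | 44 | 55 | 60 | 64 | 66 |
| t-test capped at day 30, workers | 37 | 51 | 56 | 62 | 64 |
| Chi-square day 30, workers | 42 | 50 | 49 | 40 | 27 |
| t-test, returners only | 6 | 13 | 20 | 33 | 45 |
| Chi-square, all, non-workers not returned | 31 | 30 | 23 | 13 | 7 |
| Chi-square, all, non-workers returned | 37 | 46 | 46 | 38 | 26 |

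The log-rank test is highest in every column. Its lead runs from 2 points to most of the power.

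**The case against.** The strongest reply is that the listed outcome need not be a time. Outcome 16 and Section 2.6.7 treat return to work as a status at set visits, and the time appears only as a diary item. A status at visits is categorical, so chi-square with a repeated measures model is a coherent plan. In workers that model loses only about 4 points against log-rank at 12 vs 9 days (47% against 51%), and a t-test capped at day 30 about 3. The outcome is also one part of an exploratory item with no power claim, and the log-rank test itself has only about even odds of detecting the assumed effect.

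Most of this stands, and it limits the point. A reader might infer that the comparison loses most of its power, or that patients not yet back are lost or miscounted. The documents do not support either as a general statement. Both hold only under particular choices, such as returners only or non-workers counted as not returned, and no section prescribes those. The denominator is unstated rather than wrong; the term for returning to employment itself suggests prior work. Nor does follow-up of this outcome end at day 30: only the daily record does, since it is asked again at 6 and 12 months.

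What the reply does not remove is that the time is collected, no rule covers its censoring, and nothing excludes the weak analyses. The capped t-test also needs every patient who has not returned to be followed to day 30, which the simulations assume and the plan does not.

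**Conclusion.** The point holds as a gap in the analysis plan, and correcting it is a free improvement. Return to work is recorded as a right-censored time, Aim 4 names no method for one, and no baseline-working denominator is set. Under the assumed inputs the best analysis has 44-56% power and the weakest permitted ones 8-31%, with sensible analyses in workers in between. These figures are illustrations: they rest on assumed employment and return rates, proportional hazards and complete diaries. The log-rank test's lead would shrink or could reverse if hazards were far from proportional. The outcome is exploratory, so the primary conclusion on opioid tablets is not affected.

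**What to change.** Add to Section 2.8, Aim 4, before unblinding:

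*Time to return to work will be compared by Kaplan-Meier, log-rank test and Cox model among patients working or volunteering at baseline, censored at the last diary; time to return to normal activities likewise in all patients; proportions back at work at 30 days, 6 and 12 months will be reported in the same baseline-working denominator.*

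The chi-square and repeated measures analyses can stay for status at the visits, in that same denominator. The cost is a sentence of analysis wording. Baseline employment, the daily diary and the later surveys are already in the protocol, so no new data, visits or patients are needed.

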### **3.0 Recruitment strategy and feasibility**

Subjects will be 18-65 yr. Because this is the first evaluation of methadone for outpatient anesthesia, children and older patients will not be studied (because of declining methadone elimination and increased risk of respiratory depression with age). Such studies may ensue after safety is established in the present investigation. Sample size calculations show that 300 evaluable (completing 30d follow-up) patients are needed in each of the 2 study cohorts (600 total). Change in scheduled operation, prolonged ( $>1$ d) stay of scheduled short-stay (next day discharge) patients, unanticipated admission of same-day patients, or patient withdrawal has occurred in  $\sim 10\%$  of our study patients to date. This, combined with post-op loss to follow-up (see below), suggests a potential overall drop-out rate before completion of 30d follow-up of  $<15\%$ . Hence, to ensure 300 pts evaluable at 30d, a conservative 25% drop-out is estimated and 375 pts in each of the 2 study cohorts will be randomized (750 total). The Duke Department of Anesthesiology provides anesthetics for  $>66,000$  procedures per year. The main campus of Duke University Health System includes Duke University Hospital which is a 957 bed facility. In 2016 there were 41,408 patients admitted and 1,119,151 outpatient visits. Duke University Hospital includes the Duke North Hospital/Duke Medical Pavilion ( $\sim 54$  ORs), the Children’s Health Center, the Duke Eye Center (6 ORs), and Ambulatory Surgery Center (9 ORs). Between the Duke North Hospital/Duke Medical Pavilion and Ambulatory Surgery Center there were 34,492 anesthetics performed in 2017. These included, for example, 375 laparoscopic cholecystectomies and 269 laparoscopic hysterectomies  $\pm$  salpingoophorectomies, further supporting specific feasibility. If enrollment lags, or for strategic advantage, Duke Regional and/or Duke Raleigh Hospitals can be added as future sites.

### **4.0 Management of Intercurrent Events**

#### **4.1 Adverse Experiences**

The investigator will closely monitor subjects for evidence of adverse events. All adverse events will be reported

and followed until satisfactory resolution. The description of the adverse experience will include the time of onset, duration, intensity, etiology, relationship to the study drug (none, unlikely, possible, probable, highly probable), and any treatment required.

#### **4.2 Premature Discontinuation**

If a subject withdraws from the study before the administration of study drug, or there is a protocol violation, the subject will be replaced in order to provide the required number of subjects. Dropouts and withdrawals (after study drug administration) will not be replaced, in case this is not random but outcome-related. Subjects will be withdrawn if the investigator decides that discontinuation is in the best interest of the subject, or the subject requests withdrawal from the study.

#### **4.3 Potential Risks**

Risks of being in this study are not materially different from those of surgery and anesthesia in general. Clinical opioid side effects are expected to be no different between the various opioids administered during and after anesthesia. The most common side effect of intraoperative and postoperative opioids such as methadone, fentanyl, hydromorphone and morphine is mild sedation, the magnitude of which is not different between the various opioids to be used, at the expected doses. The most common adverse effect of opioids is nausea and/or vomiting, which is not different between the various opioids to be used. Postoperative nausea and/or vomiting are also influenced by other drugs used intraoperatively. Respiratory depression is a potential concern with all opioids, but has not been problematic or different between opioids at the doses of methadone that have been used in similar previous studies, and not materially different than that from morphine, fentanyl and hydromorphone. Clinical data are collected for all enrolled patients, so there is also a potential risk of breach of protected health information.

#### **4.4 Procedures to Minimize Potential Risks**

a. Recruitment and Informed Consent. The study will be conducted under appropriate Duke University IRB protocol and consent form approvals. The study will be conducted under the supervision of the PI, who is a Board-Certified anesthesiologist with decades of experience in the conduct of human volunteer studies, and Co-Investigators, who are Board-Certified Anesthesiologists or Surgeons. Potential subjects will be approached in the pre-operative assessment clinic, or identified through IRB-approved review of the surgical schedule prior to their surgery, at which time they will be contacted and asked if they are interested in participating. An IRB-approved phone screen will be conducted and a consent visit scheduled in advance of surgery for subjects that wish to participate. This visit may also occur on day of surgery when allowing sufficient time for explanations, questions and answers. If interested and willing, subjects might also be fully consented using IRB approved eICF. All enrolled subjects must provide informed consent, evidenced by signing an informed consent document.

b. Protections against Risk.

i) Eligibility criteria exclude patients with known renal or hepatic disease, which may affect opioid disposition, as well as pregnant or nursing females. Patients with known history of hypersensitivity to opioids or, conversely, are opioid tolerant (e.g. preoperative methadone therapy or use of fentanyl or buprenorphine transdermal patches) are also excluded. For safety reasons, children and patients older than 65 yr are not studied, because of declining methadone elimination and increased risk of respiratory depression with age.

ii) Methadone dosing is fixed, using ideal body weight, rather than actual body weight, to obviate risk of excessive dosing due to obesity. The investigational pharmacist will be unblinded.

iii) Patients will have only clear liquids 6 hours before anesthesia, per standard of care. If nausea and/or vomiting occur, they will be treated using the standard of care for all post-anesthesia nausea and vomiting. Mild respiratory depression is defined as respiratory rate <8/min in adults. Severe depression will be defined as a patient with respiratory rate < 6/min. If treatment is required, naloxone will be used. Patients in the hospital are routinely periodically monitored by blood pressure and/or pulse oximetry, and receive supplemental oxygen if dictated, according to standard anesthesia practice.

iv) Research subjects will receive pre-operative, intra-operative and post-operative routine monitoring by anesthesiology and nursing staff.

- v) The risk of breach of protected health information will be minimized by limiting the number of people within the research group who have access to identified data. Data are collected and stored via REDCap. The REDCap servers are securely housed in an on-site limited-access data center managed by the Division of Biostatistics. All web-based information transmission is encrypted, and the data is stored on a private, firewall protected network. No identifiable data will be stored on personal computers or laptops. Data will be exported from REDCap for statistical analysis with patient identifying information removed. The consent form, medical information, flowsheets, will be stored under lock and key (office, file cabinet) and only the PI, physician investigators, and research team will have access.
- vi) With regard to determination of CYP2B6 (or other) genotype: 1) CYP2B6 is not associated with any disorder(s), syndrome(s), or adverse condition. 2) Samples will be kept confidentially. They will be coded, with a key to the code linking code numbers to names kept at a separate location, under lock and key. 3) The link to identifiers will be destroyed at the end of the study. 4) Testing will not provide evidence of previously undiagnosed or unrecognized illness, or susceptibility to illness. 5) Samples will not be used for any purpose other than to study genes related to study drug disposition and response. 6) Blood samples will not be used to establish permanent cell lines. 7) Data will be stored under lock and key (office, file cabinet) and only the investigators will have access. If data are published, there will be no link to identifiers. Study data will not be revealed to any organization, individuals other than the subjects, or the subjects themselves. 8) Genetic study data will not be entered in subjects' medical records. 9) Studies are not likely to result in findings that meet the National Bioethics Advisory Commission criteria for disclosure. 10) Genetics counseling will not be available to subjects, as they will not be informed of results and there are no known implications with respect to disease. 11) DNA samples will be stripped of identifiers and given a separate code numbers unrelated to the subjects' study identification numbers. The code key will be kept by the PI under lock and key.

